9 METHODS

9.1 Study Design

This is a prospective, non-randomized, single-arm study of the *da Vinci*® robotic surgical system in subjects undergoing latissimus dorsi muscle flap harvest procedures in conjunction with breast, scalp, upper extremity and lower extremity reconstructive procedures. This study will be conducted at MD Anderson in Houston, Texas. Muscle flap failure and donor site complications will be assessed through 6 months post-procedure. Flap viability will be assessed following completion of the robotic-assisted harvest procedure. Flap viability is defined as having a pink, non-congested appearance and an audible arterial and venous Doppler signal. Additional assessments of viability will include bleeding at the distal extremes of the muscle when cut sharply, and an audible Doppler signal detected in the distal third of the muscle.

9.2 Study Duration

This study is expected to commence in the first quarter of 2015. Enrollment of all subjects is expected to be completed in the second quarter of 2017. Six month clinical follow up is expected to be completed within the fourth quarter of 2017.

9.3 Number of Subjects

Fifteen subjects \geq 18 years of age, meeting all inclusion and exclusion criteria will be enrolled. Subjects will undergo robotic-assisted latissimus dorsi muscle harvest in conjunction with a standard surgical breast, scalp, upper extremity, or lower extremity reconstructive procedure requiring free or pedicled flaps.

9.4 Eligibility Criteria

9.4.1 Inclusion Criteria

Subjects must meet all of the following criteria to be eligible for enrollment in this trial:

- 1) The subject must be equal to or greater than 18 years of age.
- 2) The subject must be willing and able to provide informed consent.
- 3) The subject is willing and able to comply with the study protocol.
- 4) The subject is undergoing one of the following reconstructive procedures that requires latissimus dorsi muscle harvest:
 - a. Post-mastectomy breast reconstruction procedure (either nipple or skin sparing) in which a female subject needs additional muscle coverage over an implant, but does not need additional skin (i.e., patient is a candidate for a pedicled latissimus dorsi muscle flap procedure);
 - b. Scalp reconstruction procedure in which the subject needs a free latissimus dorsi muscle flap for wound coverage;
 - c. Upper extremity reconstruction in which the subject needs a free latissimus dorsi muscle flap for wound coverage; or,
 - d. Lower extremity reconstruction in which the subject needs a free latissimus dorsi muscle flap for wound coverage.
- 5) The subject agrees to follow up examinations out to 6 months post-treatment.

9.4.2 Exclusion Criteria

Subjects will be excluded from this trial if any of the following criteria are met:

- 1) The subject has a BMI > 35.
- 2) The subject has a history of significant bleeding disorders.
- 3) The subject is diabetic.

- 4) The subject is known or suspected to be pregnant or lactating.
- 5) The subject has a history of peripheral vascular disease.
- 6) The subject is a current smoker (has smoked within 4 weeks prior to surgery).
- 7) The subject has had prior back or axillary surgeries which could compromise the blood supply of the flap.

9.5 Withdrawal of Subjects

Subjects may voluntarily withdraw their participation from the study at any time. Investigators may withdraw a subject from the study as deemed appropriate per safety measures and/or if the subject's medical condition contraindicates further study participation. All subjects withdrawn from the study will undergo a final study visit consisting of a safety evaluation.

9.6 Evaluation Tests

The disabilities of the arm, shoulder and hand (QuickDASH) questionnaire is a self-administered outcome instrument developed as a measure of self-rated upper extremity disabilities and symptoms (Appendix E). The QuickDASH consists of 11 items scored 0 (no difficulty) to 5 (unable/extreme) with 8 optional occupational questions. It has been validated for longitudinal construct and been rated effective as a post-surgery measurement tool.¹¹

The validity of VAS has been well studied for eliciting reproducible pain assessments^{12,13,14}. In pain research VAS are considered 'the gold standard' for pain assessments. Subjects report their level of pain through the scale. A copy of the VAS is located in Appendix F.

The functional evaluation of the shoulder uses the American Shoulder and Elbow Surgeons (ASES) method which is a standardized form for shoulder assessment¹⁷. The physical therapy assessment section includes range of motion and strength. While a comparison is regularly made between the operated versus non-operated shoulder, for this study, the subject will have an initial baseline test done preoperatively to compare with the postoperative evaluation. The measurement of active and passive range of motion and the manual muscle-testing will be performed on all subjects by a member of the Physical Therapy staff. Shoulder mobility is expressed in degrees with abduction, adduction, intra-rotation and extra-rotation measured both actively and passively. A sample of the range of motion and strength forms are located in Appendix G.

10 RISK-BENEFIT ASSESSMENT

10.1 Risks

As part of the robotic-assisted muscle harvest procedure the thoracodorsal nerve may sometimes be intentionally sacrificed resulting in a known risk of impaired range of motion (internal rotation and abduction of the arm <90 degrees). Pneumothorax from unintentional entrance into the pleural space is also a potential risk but very rarely occurs in either open or endoscopic muscle harvest^{1,5,16}. Clinically detectable postoperative pneumothorax will be managed in consultation with the thoracic surgery service. Management will include chest tube placement and monitoring with serial upright and lateral chest x-rays. Pneumothorax has not been present in the over 30 clinical cases thus far. In order to detect unintended pneumothorax, the muscle donor site cavity will be subjected to positive pressure ventilation by the anesthesiologist to insure that no small pneumothorax has occurred. In the event of a pneumothorax detected intraoperatively, the anesthesiologist will be made aware immediately and an intraoperative consult to a thoracic surgeon will immediately result. If a chest tube or catheter is deemed necessary, it will be placed at that time under direct vision by a board certified thoracic surgeon.

In addition, there are other standard risks associated with any latissimus dorsi harvest procedure independent of the method of harvest. These include: 1) postoperative pain; 2) bleeding which may require transfusion; 3) infection at the donor or transfer site; 4) numbness or tingling; 5) thrombosis of the pedicle; 6) scarring, wound dehiscence, or delayed wound healing at the incision site; 7) partial or total flap necrosis or loss; 8) pulmonary embolism; 9) inflammatory syndrome; and, 10) swelling, seroma or hematoma at the donor site. These will all be managed according to standard hospital procedures.

Potential risks that are unique to endoscopic harvest include subcutaneous emphysema as a result of insufflation, and bleeding which cannot be managed endoscopically. Subcutaneous emphysema with CO₂ requires no additional postoperative management as it resolves quickly and is not in a position to impinge on the airway^{18,15}. Bleeding that cannot be managed endoscopically may be controlled with direct external pressure and conversion to open techniques, when necessary. This has not occurred in any of the robotic harvests to date, and it is believed that hemostasis will be easier to maintain and regain with robotic instruments than with standard endoscopic techniques.

Additional risks presented by use of the *da Vinci*® robotic surgical system other than those listed above include the possibility of a device malfunction which may require a conversion to an open procedure. If the system is unavailable for use or other clinical factors proscribe system use, the physician may convert to a standard open surgical procedure.

There are also small additional risks associated with the patient being under anesthesia for a longer period of time which will be required given the slightly longer length of time expected for robotic-assisted procedures when compared with open techniques. However, early clinical work has already shown lower operative times with the *da Vinci*® robotic surgical system than previously reported endoscopic harvests.

The above referenced risks will be mitigated in two ways. First, [name] and [name], both experienced plastic and reconstructive surgeons, who have been extensively trained on the *da Vinci*® robotic surgical system, will be the only two surgeons performing procedures under this study protocol.

10.2 Benefits

There is no proven benefit related to use of the *da Vinci*® robotic surgical system for latissimus dorsi muscle harvest surgical procedures. It is hoped that the investigational device will permit a simpler, minimally invasive harvest technique with smaller incisions, decreased postoperative time and a quicker return to normal activities. However, the device has not yet been studied to demonstrate its utility in this regard. Subjects may benefit from the additional clinical monitoring and follow up evaluations required by this study protocol.

11 STUDY PROCEDURES

11.1 Subject Screening and Baseline Evaluation (Visit 1)

Subjects will be recruited for this study from MD Anderson. All subjects requiring latissimus dorsi muscle harvest procedures in conjunction with breast, scalp, upper extremity, or lower extremity reconstruction procedures will be screened for eligibility. The Investigator or a member of the research team will review the subject's medical history for eligibility and inclusion into the study. If all inclusion criteria are met and no exclusion criteria are present, the Investigator will inform the subject about the purpose of the study and will obtain written informed consent. The background of the proposed study along with the benefits and risks will be explained to the subject and questions will be answered. The subject must sign an informed consent that has been approved by the MD Anderson Institutional Review Board (IRB). Failure to provide informed consent renders the subject ineligible for the study.

The Investigator or a member of the research team will record the subjects' medical history and demographic information on a case report form tool. Protocol specific data and adverse events will be entered into the MD Anderson REDCap™ database. The first assessment of adverse events will take place in the operating suite at the time of surgery

and will continue for 6 months following surgery. The medical history will include information about previous treatments to further ensure compliance with the inclusion and exclusion parameters. The Investigator will conduct a medical history review and a physical exam. A pre-anesthesia appointment will also be coordinated. The Investigator or a member of the research team and subject will also complete a QuickDASH questionnaire. The subject will also undergo a physical therapy assessment to test the range of motion and strength of the shoulder to be used as a baseline postoperatively. As standard of care for patients undergoing these procedures, a pregnancy test will be ordered by the Anesthesia Department for appropriate female patients. This visit may be completed within 30 days prior to treatment/surgery.

11.2 Treatment (Visit 2)

The subject will be taken to the operating room for surgery under general anesthesia with no muscle paralysis. The robotic-assisted latissimus dorsi harvest procedure will be performed as described in the protocol and will be videoed and/or photographed. Medications used, port placements, procedural details, adverse events and device details will be documented on the CRFs (Appendix H). Muscle flap viability will be assessed by clinical examination and doppler assessment prior to the reconstruction procedure. Such assessments will be documented in the CRFs (Appendix H) prior to the standard surgical breast, scalp, upper extremity, or lower extremity reconstruction procedure.

11.3 Follow Up Evaluations (Visits 3-6)

Patients will be seen in the office for a visit within 0-2 weeks and then within 2-4 weeks after the surgical procedure. The next visit will be between 1-3 months after the procedure. The final visit will be between 3-6 months after the procedure. At these postoperative visits, incisions and drain sites will be checked and donor sites will be evaluated for adverse events. Additionally, pain assessments, the QuickDASH questionnaires, and the range of motion and strength tests will be administered. Drains will be removed as appropriate at approximately 2 to 3 weeks after the procedure.

11.4 Schedule of Events

The protocol does not require any clinic visits other than those that are standard of care for patients undergoing robotic-assisted harvest of the latissimus dorsi muscles.

Study Events	Screening & Baseline Evaluation (Visit 1) ¹	Procedure / Treatment (Visit 2)	Post Op Follow Up (Visits 3-6) ^{2,3}
Eligibility Screening	X		
Secure Informed Consent	X		
Medical History and Physical Exam (to include BMI)	X		

Pre-Anesthesia Appointment (to include Urine Pregnancy Test - if appropriate per Anesthesia)	X		
Baseline QuickDASH Questionnaire	X		
Baseline Physical Therapy Assessment (to include testing range of motion and strength of the shoulder)	X		
Robotic-Assisted Latissimus Dorsi Flap Harvest Procedure & Non-robotic Reconstruction Procedure		X	
Flap Viability Assessment via Clinical and Doppler Examinations		X	
Adverse Event Assessment		X	X
Postoperative QuickDASH Questionnaire			X
Postoperative Physical Therapy Assessment (to include testing of range of motion and strength of the shoulder)			X
Patient Questionnaire of Pain via VAS			X
Drains Removed			X

¹ Occurs within 30 days prior to surgery.

² Visit 3 (occurs between 0-2 weeks), Visit 4 (occurs between 2-4 weeks), Visit 5 (occurs between 1-3 months)

³ Final Visit (occurs between 3-6 months)

12 STATISTICAL ANALYSIS PLAN

This is a prospective, non-randomized, single-arm study designed to assess the safety and feasibility of the *da Vinci*® robotic surgical system in latissimus dorsi muscle flap harvest procedures. A maximum of 15 subjects requiring latissimus dorsi flap harvest procedures in conjunction with breast, scalp, upper extremity, or lower extremity reconstruction procedures will be enrolled at MD Anderson in Houston, Texas.

The muscle flap failure will be monitored using the Bayesian stopping boundaries calculated based on beta-binomial distribution. We will consider that the *da Vinci*® robotic surgical system is promising in latissimus dorsi flap harvest if the muscle flap failure rate is below 10%. With a sample size of 15 patients, the probability of observing at least one muscle flap failure is 79.4%. The prior probability of muscle flap failure is modeled by beta distribution (Beta (0.1, 0.9)). Denoting the probability of muscle flap failure by θ , and it is compared to fixed target of 10%. The following decision criterion will be applied: Stop if $\text{Prob}\{\theta > 0.10 \mid \text{data}\} > 0.75$.

Patients will be monitored by a cohort size of 5 according to the following stopping boundaries for muscle flap failure. The patient enrollment will be halted for this safety monitoring because the status of muscle flap failure can be obtained right after surgery.

Number of patients evaluated	Stop if \geq muscle flap failure observed
5	2-5
10	2-10
15	Always stop with this many patients

The operating characteristics are summarized in the following table (based on simulations from 10,000 trials).

True DLT Rate	Prob (stop the trial early)
0	0
0.05	0.0861
0.10	0.2639
0.15	0.4557
0.20	0.6242
0.25	0.7560
0.30	0.8507

The above stopping boundaries and operating characteristics are calculated using MultcLean (v.2.1.0) design software downloaded from <http://biostatistics.mdanderson.org/SoftwareDownload>.

The muscle flap failure rate and its 95% confidence interval (CI) will be calculated using the exact method. Other outcome data to be collected will include: pain assessment using a validated VAS, QuickDASH score, and physical therapy assessment.

Patient information including age, gender, body mass index (BMI), medical history, history of radiation, history of smoking, defect characteristics (such as "partial breast, scalp, upper extremity, or lower extremity"), donor site morbidity, and functional deficits will be summarized. The rate of donor site morbidity and their 95% confidence interval will be reported.

Operative Variables: Length of surgery, type of defect, size of defect, type of reconstruction, length of incision used, length of robotic portion of the procedure, robotic instrumentation used, port placement. This information will be documented by the OR staff during surgery, and collected by the research team after surgery on standardized CRFs.

Outcome Variables: Length of stay, pain medication requirements, postoperative complications (such as seroma, wound dehiscence, delayed wound healing, or flap loss), length of time drains are required in donor site, and postoperative return to normal function, as well as, any residual functional deficits, defined as a subjective decrease in strength, range of motion or restriction in activities of daily living will be assessed at

between week 0-2, and between week 2-4 after the procedure. The subject will then have an evaluation at 3 months after the procedure. The subject's last follow up visit will occur 6 months post-procedure.

The safety of the robotic-assisted latissimus dorsi procedure will also be evaluated based on adverse events related to the donor site through 6 months post-procedure. Acute complications include but are not limited to: seroma; hematoma; overlying skin damage; and, injury to the muscle or vascular pedicle. All adverse events will be further categorized and documented according to section 13 of this clinical protocol.

The feasibility of the procedure will be evaluated based on the number of successfully completed robotic-assisted latissimus dorsi harvest procedures among the total attempted procedures. Any procedure that is abandoned or converted to an open surgical or endoscopic technique after being initiated with the *da Vinci*® robotic surgical system will be considered a failed *da Vinci*® procedure. The rate of successfully completed harvest procedure will be calculated along with its 95% CI.

The efficacy of the procedure will be determined based on the rate of subjects who demonstrate a viable flap assessed by clinical and doppler examinations at the end of the harvest procedure. It is recognized that the overall success of the surgery from the patient's and surgeon's perspectives includes the success of the harvest and reconstruction procedures. However, the objective of this investigational protocol is to evaluate the robotic-assisted muscle harvest technique only. As such, flap viability prior to reconstruction is the most relevant outcome for this study. Additional secondary assessments will include: long term survival of the flap and flap necrosis at the postoperative visits. These assessments will not be employed to adjudicate the primary efficacy endpoint.

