14.7 Protocol Monitoring Plan

This is a single-arm study and, therefore, does not require MD Anderson's Data Safety Monitoring Board (DSMB) review. This study will be monitored by the MD Anderson IND Office and the Principal Investigator. A protocol-specific monitoring plan will be followed.

The trial will be stopped if flap failures are observed in 2 of the first 5 patients treated. The trial will also be stopped if flap failures are observed in 2 of the second set of 5 patients treated. Flap failure is defined as irreversible arterial and venous thrombosis detected by implantable or surface doppler signal within 72 hours after surgery. Notice will be provided to the Principal Investigator, the IRB, and the FDA should early termination of the trial be recommended. The trial will not restart until a thorough risk analysis has been completed and the FDA and IRB provide their written approval to restart the study.

15 Protocol Deviations

[name] and [name] will not deviate from the protocol except in medical emergencies. If a medical emergency occurs, prior approval will not be required but the IRB must be notified of the deviation in accordance with Chapter 25, Reporting Requirements and Timeframes of MD Anderson's IRB Policy on Reporting Protocol Deviations.

16 Device Accountability

The *da Vinci*® robotic surgical system and the corresponding instruments that will be used in this study have been FDA cleared for a variety of surgical indications. [name] and [name] will use the *da Vinci*® robotic surgical system and instruments that are currently in use at MD Anderson for other cleared clinical indications. MD Anderson will ensure that the Investigator and clinical site personnel are aware they must report any device malfunction related to this study to Intuitive Surgical within 24 hours. In addition, clinical site personnel must complete the Device Performance Issue-Malfunction case report form (Appendix H).

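### A second flap failure among patients 1-10 makes the stop certain, but Section 12 acts only at 5 and 10 patients, and Section 14.7 counts the second set differently

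*Combined protocol and SAP*

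**What the plan says.** Section 12 gives flap failure a Beta(0.1, 0.9) prior and a fixed 10% target, and stops the trial if the posterior probability of a rate above 10% exceeds 0.75. On timing it says: "Patients will be monitored by a cohort size of 5 according to the following stopping boundaries for muscle flap failure". The boundary table has 2 or more failures at 5 patients and 2 or more at 10. Its row for 15 reads "Always stop with this many patients", which is the planned end of the trial and not a failure boundary. The same section says that enrolment is halted for this monitoring and that failure status is available directly after surgery. It then tabulates the probability of stopping early for true rates from 0 to 0.30.

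Section 14.7 restates the rule. Two failures in the first five patients stop the trial, and then: "The trial will also be stopped if flap failures are observed in 2 of the second set of 5 patients treated". It defines failure by Doppler-detected thrombosis within 72 hours of surgery and gives no rule for patients 11-15. It also says that DSMB review is not required, so the written rule is the main formal safeguard.

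**The concern.** The boundary is the same number, 2, at both looks. Once two failures have occurred among the first 10 patients, no later result can prevent a stop at the next look. Any subject treated between that failure and the look is exposed without contributing to the stop decision.

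Waiting has no evident practical purpose. The outcome is known within 72 hours, and Section 9.2 runs enrolment from the first quarter of 2015, saying "Enrollment of all subjects is expected to be completed in the second quarter of 2017". If accrual is even, 15 subjects over at most 30 months is about one every 2 months, so each outcome is normally known before the next operation.

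Section 14.7 adds a second difficulty. It might be taken to mean that the trial acts when the second failure is seen, but it counts the second five patients separately. One failure in each set of five stops the trial under Section 12 and not under Section 14.7.

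**Working it through.** **Inputs.** Section 12: maximum 15 subjects, Beta(0.1, 0.9) prior, 10% target, 0.75 threshold, cohorts of 5. Section 14.7: 72-hour failure window and the per-set wording. Let p be the true failure rate, with independent outcomes.

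**1. Boundaries.** After k failures in n patients the posterior is Beta(0.1 + k, 0.9 + n - k). The probability of a rate above 0.10 is 0.641 at 1/5, 0.933 at 2/5, 0.393 at 1/10 and 0.765 at 2/10. The smallest count above 0.75 is 2 at both looks, as the plan states.

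**2. The plan's operating characteristics.** With a boundary of 2 at both looks, the trial stops early exactly when there are at least 2 failures in the first 10:

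P(stop early) = 1 - (1-p)^10 - 10p(1-p)^9.

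At p = 0.10: 1 - 0.3487 - 0.3874 = 0.2639. The other rates give 0.0861, 0.4557, 0.6242, 0.7560 and 0.8507. All match the table, so the table describes looks at 5 and 10 with a cumulative count and no other look.

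**3. Subjects treated after the second failure.** The second failure falls on patient m with probability (m-1)p²(1-p)^(m-2). The number treated before the look is 5 - m for m = 2 to 5, and 10 - m for m = 6 to 10. The maximum is 4, when the second failure is at patient 6.

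At p = 0.10, summing probability times number treated:
- m = 2 to 5: 0.0300 + 0.0360 + 0.0243 + 0 = 0.0903
- m = 6 to 10: 0.1312 + 0.1063 + 0.0744 + 0.0383 + 0 = 0.3502
- Total 0.4405 per trial; 0.4405 / 0.2639 = 1.67 per stopped trial

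| True rate | P(stop early) | Mean treated after second failure, all trials | Mean per stopped trial | P(at least one treated after) |
|---|---|---|---|---|
| 0.05 | 0.0861 | 0.14 | 1.61 | 0.063 |
| 0.10 | 0.2639 | 0.44 | 1.67 | 0.196 |
| 0.20 | 0.6242 | 1.10 | 1.77 | 0.482 |
| 0.30 | 0.8507 | 1.57 | 1.84 | 0.681 |

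Acting at the second failure leaves the P(stop early) column as it is, because the same trials stop.

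**4. Section 14.7 read per set.** Let q = P(at least 2 of 5). Then P(stop early) = 1 - (1-q)².
- p = 0.10: q = 0.0815, giving 0.156 against the stated 0.264
- p = 0.20: q = 0.2627, giving 0.456 against the stated 0.624

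The gap is the chance of one failure in each set: 0.32805² = 0.108 at 10% and 0.4096² = 0.168 at 20%.

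**5. After patient 10.** Two failures no longer exceed the threshold (0.727 at 2/11). A cumulative total of 3 does: 0.922, 0.903, 0.882 and 0.859 at 11, 12, 13 and 14 patients. The chance that the third failure falls in patients 11-14 with no stop at 10 is P(1 of 10)·P(at least 2 of 4) + P(0 of 10)·P(at least 3 of 4):
- p = 0.10: 0.3874 × 0.0523 + 0.3487 × 0.0037 = 0.022
- p = 0.20: 0.2684 × 0.1808 + 0.1074 × 0.0272 = 0.052

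Without a stop at 10 the third failure cannot come before patient 12, so at most 3 further subjects are involved. Acting on it would spare a mean of 0.04 subjects per trial at 10% and 0.09 at 20%.

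**The case against.** Cohort-wise looks are a legitimate design. The plan states its schedule, gives boundaries for it and tabulates operating characteristics that are correct for it. This stands: there is no arithmetic error here.

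Nor does any passage require a cohort to be filled after a second failure. Section 12 mentions halting enrolment for monitoring, and Section 14.7 can be read as acting when the second failure is observed. This also stands in part. The weakness is that the plan does not say so, and the passage that comes closest uses a different count.

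A reader might infer that the plan breaches its own posterior criterion whenever the probability passes 0.75 between looks. The documents do not support that. The criterion is implemented through the table at 5 and 10. If it applied after every patient, a single failure in the first 1, 2 or 3 patients (0.929, 0.850, 0.775) would also stop the trial, and early stopping at a true rate of 10% would be 0.396, not 0.264. The within-cohort argument does not need that reading. It rests only on the fact that the tabulated stop is already certain.

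For the same reason, a boundary for patients 11-14 would be an addition to the plan and not the enforcement of something it already contains. Failures in patients 11-15 still enter the final failure rate and its exact confidence interval.

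**Conclusion.** The point holds as a gap in the safety-monitoring wording, together with a real conflict between Sections 12 and 14.7. As tabulated, the rule allows a mean of 1.6 to 1.8 subjects, and at most 4, to be treated in stopped trials after the stop has become certain. Over all trials this is 0.44 subjects at a true rate of 10% and 1.10 at 20%. The conflict is material: if Section 14.7 governs as worded, the operating-characteristics table does not describe the rule in use.

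The absence of a boundary for patients 11-14 is a minor matter, crossed in about 2% of trials at 10% and 5% at 20%.

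The figures assume independent outcomes at a constant rate, subjects treated one at a time with each 72-hour outcome known before the next operation, and monitoring by the 72-hour definition in Section 14.7. Section 9.1 also speaks of assessing flap failure through 6 months. A failure recognised later than 72 hours would reduce what immediate action can spare.

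**What to change.** 1. In Section 12, state that the existing count of 2 is acted on as soon as the second failure among patients 1-10 is observed, without waiting for the cohort of 5 to be complete. Express it as a count, not as a posterior recomputed after each patient, so that one early failure does not become a trigger. This costs a sentence; every tabulated stopping probability stays the same.

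2. Reconcile Section 14.7 with the cumulative rule in Section 12, which is the one the table describes. If the per-set count is what the sponsor intends, the table must be recalculated instead (0.156 at 10%, 0.456 at 20%).

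3. Optional and of lower priority: state whether any failure boundary applies to patients 11-14. If one is added at the 0.75 threshold, word it as a cumulative total of 3 failures since patient 1, so that it cannot be read as 3 within the last five. The table must then be restated: P(stop early) goes from 0.086 to 0.091 at 5%, from 0.264 to 0.286 at 10% and from 0.624 to 0.676 at 20%.
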